- Behavior Rating Inventory of Executive Function (BRIEF2/P), a measure of executive function (the global score a co-primary outcome). The BRIEF-P is for use in pre-school children.
- Child Behavior Checklist (CBCL), a measure of behavior
- Conners Third Edition Short Form, a measure of attention-deficit/hyperactivity disorder symptoms (parents of children \geq 6 years of age only)
- Adaptive Behavior Measure System, 3rd Edition (ABAS-III), a measure of children's everyday functioning (this measure is centrally scored, and date of birth as well as date of study and study ID is required to be entered into the WPSpublish website)

- Epworth Sleepiness Scale modified for children, a measure of daytime sleepiness
- Pediatric Quality of Life Inventory (PedsQL; parent form), a generic measure of global quality of life
- OSAS-18, a measure of disease-specific quality of life
- Pediatric Sleep Questionnaire Sleep-Related Breathing Disorder Scale (PSQ-SRBD scale), a measure of symptoms of SDB, including nighttime and daytime symptoms.
- Family Assessment Device, a measure of family functioning
- Parenting Style Questionnaire, a survey of the type of parenting style
- Parenting Stress Index 4th Ed., Short Form, a measure of parents' perception of stress
- Rapid Estimate of Adult Literacy in Medicine, Revised, a measure of patient (caregiver) health literacy (only at baseline visit)
- Experiences of Discrimination, a measure of experiences with racism
- International Study Of Asthma And Allergies In Childhood (ISAAC), a survey to determine the presence of asthma, rhinitis and eczema
- Asthma Severity Survey, a measure of asthma exacerbations and controller therapy based on items from the Composite Asthma Severity Index (only for children with ISAAC Global Wheezing Score ≥ 5)
- COVID-19 Survey

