9.7.1. Screening visit/PSG eligibility – Day -60 to -1

At this visit, preliminary study eligibility is confirmed and informed consent obtained. If the participant had a clinical PSG, then these data are sent to the DCC/ Reading Center to confirm eligibility. If the participant has not had a PSG, then a research PSG is performed.

9.7.2. Baseline visit – Day 0

After PSG eligibility for MSDB is confirmed, this visit includes anthropometry, BP measurement and physical examination. The child completes behavioral performance measures and the parent completes questionnaires about behavior & attention, SDB symptoms, sleepiness, quality of life and family functioning. Children \geq 5 years of age also complete the child version of the PedsQL. Urine is collected for cotinine and serum

IgE is collected by venipuncture. The research coordinator inquiries about adverse events, changes in health status or medication, and HCU. Eligibility is confirmed and the participant is randomized. Behavioral rating scales are mailed to teachers.

9.7.3. Monthly Check-In – Months 1, 2, 3, 4, 5, 7, 8, 9, 10, 11

Between each face-to-face visit, study staff will make contact by telephone, email and/or text messaging, with families in both groups for inquiries about adverse events, medications, and changes in health status using a study CRF. HCU is assessed and EMR surveillance completed. Participants are reminded about upcoming study visits and study participation is reinforced.

9.7.4. Remote Interim Visit – Month 6

The parent completes questionnaires about behavior, SDB symptoms, sleepiness, quality of life and family functioning. Study staff inquire about adverse events, changes in health status or medication, and HCU. EMR surveillance is completed. Behavioral rating scales are mailed to teachers. Note that with the Covid-19 pandemic, 6 month visits can be held virtually if in-person visits are not possible, focusing on parent-related questionnaires.

9.7.5. Endpoint PSG – Month 12

Participant completes overnight PSG using the same protocol as for baseline PSG.

9.7.6. Endpoint daytime visit – Month 12

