This visit includes measurement of anthropometry, BP and behavioral performance testing. Parent completes questionnaires about behavior and attention, SDB symptoms, sleepiness, quality of life and family functioning. Participants \geq 5 years also complete the child version of the PedsQL. Study staff inquire about adverse events, changes in health status or medication, and HCU. Behavioral rating scales are mailed to teachers. Participants in the WWSCL arm are scheduled for re-evaluation with their ENT surgeon within 1-4 weeks if indicated.

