Aim 3 is to identify factors that moderate the behavior and health care utilization changes in response to surgery (AT). As described in the CCC application, we anticipate that 50% of children will be age less than 5 years; 47% will be overweight/obese; 40% will be African American (AA), 30% will have asthma, and 20% will be exposed to secondhand smoke. The study will have 80% power to detect a treatment effect difference of 0.58, 0.59, 0.60, 0.64, and 0.74 standard deviations for interactions between treatment and age, overweight/obese, race, asthma, and secondhand smoke, respectively. In the CHAT study, the estimated difference in treatment effect on BRIEF

GEC score between AAs and non-AAs was 4.63 and the estimated standard deviations in the 4 subgroups defined by treatment and race ranged from 7.69 to 9.27. Assuming that the difference in treatment effect between AAs and non-AAs is 4.63 and a standard deviation of 9, a sample size of 184 per treatment group with 40% AAs provides 67% power to detect this difference (a 0.51 standard deviation of treatment effect difference) based on normal approximation at the 5% significance level.

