Aim 2: For endpoints related to HCU (illness or injury requiring hospitalizations; emergency department visits; inpatient procedures; outpatient procedures; scheduled office visits; unscheduled office visit or urgent care visits; medication use), incidence rate per person will be calculated. Recognizing that these count data are likely to be non-normal and skewed, we will use Wilcoxon rank-sum tests to compare study groups. To better model the underlying distribution of the count data and take into account potential data dispersion and possible preponderance of zeros, we will use goodness of fit statistics (e.g., AIC/BIC), likelihood ratio tests or the Vuong test⁸² to choose among the zero-inflated negative binomial models, zero-inflated Poisson models or regular negative binomial models. The models that best fit the data will be used to model treatment effect adjusting for covariates. Incidence rate ratios comparing treatment groups will also be reported. We also will describe distributions of medication classes (e.g., antibiotics, nasal anti-inflammatory medications, asthma medications) and reasons for hospitalizations, etc. by group to identify reasons for HCU differences (e.g., infection; respiratory illness). Analyses will be performed both including and excluding events associated with the intervention (surgery and pre- and post-operative care, but not include the polysomnography).

Aim 3: Whether treatment effects pertain to some subgroups and not to others are of great clinical significance. Statistical tests of treatment by covariate interaction will be performed to assess whether treatment effect varies by age, baseline weight, atopy/asthma status, secondhand smoke, socioeconomic status, family functioning, baseline symptom severity (e.g., Sleep Disordered Breathing Scale) or race. Within the group of children with asthma, we will assess whether asthma exacerbations differ by treatment group, using similar approach for count data as described in the analysis for HCU indices.

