If we identify race differences in treatment effects, we will explore whether those differences are explained by the measured social and environmental factors, such as measures of family functioning or secondhand smoke exposure. To address this question, we will use models similar to the mediated baseline by treatment interaction models proposed by Baron and Kenny⁸⁴ and MacKinnon⁸⁶, except that the mediators under consideration will be those measured social and environmental factors mentioned above. More specifically, we will fit the following models: (1) $Y = i_1 + c_1 X + c_2 Z + c_3 XZ + e_1$; (2) $Y = i_2 + c'_1 X + c'_2 Z + c'_3 XZ + bM + e_2$; (3) $M = i_3 + a_1 X + a_2 Z + a_3 XZ + e_3$, where Y denotes the outcome (e.g., BRIEF2/P GEC change score or GNG change score), X denotes the

treatment indicator, Z denotes race, and M denotes the potential mediator (measured social and environmental factor under consideration) for the racial differences in treatment effects (c_3). Our interest here is to explore the potential mediation effects corresponding to the effect of XZ to M to Y, through evaluating the significance tests for \hat{c}_3 , \hat{a}_3 , \hat{b} , and \hat{c}_3 (or $\hat{a}_3\hat{b}$), the estimates of corresponding regression coefficients.

One gap in the CHAT study was lack of objective data on nightly sleep duration, which may significantly influence behavior and cognition. In this study, we will evaluate whether baseline average nightly sleep duration and continuity obtained from in-home actigraphy are associated with: a) baseline behavior and performance measures; b) whether there is an interaction between sleep duration and treatment. Models will be similar to those described above. We also will evaluate whether changes in sleep duration and continuity are associated with changes in behavior and performance outcomes.

Impact of Coronavirus Disease 2019 (COVID-19) Pandemic

We will summarize data quality and missingness by whether the relevant visit (at baseline, 6 months, or 12 months) occurred (or was scheduled to occur) prior to or following 03/11/2020, the date on which the World Health Organization declared COVID-19 to be a global pandemic.

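### The Aim 3 models for explaining a race difference in benefit cannot credit a factor measured only at baseline, such as urinary cotinine, except by chance

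*Combined protocol and SAP*

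**What the plan says.** The Aim 3 text in section 19 (Secondary Analyses) says that, if race differences in treatment effect are found, "we will explore whether those differences are explained by the measured social and environmental factors", with family functioning and secondhand smoke as its two examples. It prints three models, with X for treatment, Z for race and M for the factor:

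1. Y on X, Z and XZ (interaction coefficient c3)
2. Y on X, Z, XZ and M (interaction coefficient c3', coefficient b for M)
3. M on X, Z and XZ (interaction coefficient a3)

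The aim is stated as "Our interest here is to explore the potential mediation effects corresponding to the effect of XZ to M to Y", judged by c3, a3, b and the product a3·b. No visit is given for M.

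Timing has to be read from the protocol:

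- **Secondhand smoke.** Section 3.3 defines it by urinary cotinine. Section 9.7.2 places the sample at Day 0 ("Urine is collected for cotinine and serum" IgE drawn), and Appendix A marks it at baseline only. Section 9.3 puts randomization at the end of that visit.
- **Health literacy.** Section 9.2.7 also limits this to baseline.
- **Family functioning.** This is repeated at month 6 (section 9.7.4) and month 12 (section 9.7.6): "Parent completes questionnaires about behavior and attention, SDB symptoms, sleepiness, quality of life and family functioning".

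Separately, Aim 3 plans single-factor interaction tests: "Statistical tests of treatment by covariate interaction will be performed to assess whether treatment effect varies by age" and other factors, including secondhand smoke, family functioning and race.

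**The concern.** The printed models suit a factor that treatment changes, and changes differently by race. A factor fixed before randomization cannot act that way. It accounts for a race difference in benefit by another route: it is distributed differently by race, and it modifies the treatment effect. That route needs a treatment-by-factor term, XM, and none of the three models has one. The protocol itself treats these variables as modifiers: section 3.3 lists cotinine among potential effect modifiers.

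What is at stake is the SAP's own question. For a baseline-only factor, a report that it does not explain the race difference would follow from the model form and not from the data.

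**Working it through.** **The SAP's figure.** The only stated number tied to c3 is the 67% power in Estimated Power and Sample Size: "Assuming that the difference in treatment effect between AAs and non-AAs is 4.63 and a standard deviation of 9", 184 per arm, 40% African American, 5% level. The 4.63 follows from Table 1: (-1.82 + 0.30) - (-4.98 - 1.17) = -1.52 + 6.15 = 4.63. The arm-by-race cells hold 184 × 0.4 = 73.6 and 184 × 0.6 = 110.4 children.

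- SE = 9 × √(2/73.6 + 2/110.4) = 1.915
- Power = Φ(4.63/1.915 - 1.96) = Φ(0.457) = 67.6%, which agrees with the SAP.

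**The algebra.** Substitute fitted model (3) into fitted model (2). The coefficient of XZ becomes c3' + b·a3. The residual of (3) is orthogonal to X, Z and XZ, so this must equal c3 from model (1). On the same children, therefore, c3 - c3' = a3·b exactly.

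Model (3) is saturated in X and Z, so a3 is the eAT-minus-WWSC difference in mean M among African American children, minus the same difference among the others. If M is fixed before assignment, each difference is zero in expectation. Minimization on race does not change that. So c3' equals c3 on average, whatever M truly explains.

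With XM in the model (coefficient d), the race difference in treatment effect is c3' + d × (race gap in M). The second part is what the factor explains.

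**Size, by simulation.** There were 2,000 to 4,000 runs per setting.

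- From the SAP: n = 368, 40% African American, race difference 4.63, residual SD 9, overall smoke exposure 20%.
- Assumed, because the documents give no values by race: a continuous M with a race gap of 0.5, 0.8 or 1.2 SD, or smoke exposure of 10% against 35% (0.6 × 10% + 0.4 × 35% = 20%).
- Assumed true share explained: 25%, 50% or 100%.

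In the table, the last column is the proportion of runs with a3 and b both significant at 5%.

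| M | True share | c3 | c3' as planned | c3' with XM | Path found |
|---|---|---|---|---|---|
| Baseline, gap 0.8 SD | 100% | 4.62 | 4.62 | -0.02 | 4.8% |
| Baseline smoke | 50% | 4.63 | 4.63 | 2.31 | 6.7% |
| Baseline smoke | 100% | 4.58 | 4.58 | -0.02 | 7% |
| Baseline smoke | 0% | 4.60 | 4.60 | not run | not run |
| Changed after randomization, 0.8 SD | 100% | 4.69 | 0.05 | not run | 96% |

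Across all baseline settings with a true share of 25% or more:

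- The planned models credit -0.5% to 0.4% of the difference on average, and the path is found in 0.8% to 7.7% of runs.
- With XM the credited shares are 24-26%, 49-50% and 99-102% for true shares of 25%, 50% and 100%.
- Giving continuous M a main effect of 2 points per SD (shares 50% and 100%) changes nothing.
- The identity held to 1e-13.

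The analysis runs only if a race difference is found. Among runs with significant c3, the planned models credit 0.1% to 5.0%. With XM the shares are 20-21%, 41-42% and 80-82%; they fall short because c3 is inflated by that selection. For gap 0.8 and share 100% (2,354 of 4,000 runs), c3 is 6.01, c3' as planned 5.89, and c3' with XM 1.14.

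**The case against.** The algebra is not in dispute. The best counter-case has four parts.

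**Both ingredients are already planned.** Model (3) yields a2, the race gap in M, and the single-factor tests cover treatment by smoke. In simulation both are significant in 91-100% of runs at a true share of 100%, 85-98% at 50%, and 8-24% at 0%. So a reader could tell all from none. But the SAP neither lists a2 among its tests nor describes combining it with the other result. Nor does the combination measure the share. The product of the race gap and the single-factor interaction averages 0.3 to 1.2 points when the factor explains nothing, up to 1.2/4.63 = 26% of the difference. The interaction test alone is no guide either: it flags a modifier with no race gap in 85-100% of runs (2.9 or 5.8 points per SD), although that factor explains none of the difference.

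**The fix is imprecise at small shares.** This stands. At a true 25%, the drop in c3 with XM averages 1.1-1.2 points with SD 0.6-1.1, and XM is significant in only 16-67% of runs.

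**Full explanation is implausible.** This also stands. With a 25-point exposure gap, smoke would have to change the treatment effect by 4.63/0.25 = 18.5 points, about twice the SD of 9 and five times the expected overall effect of 3.7. For a continuous factor it takes 4.63/1.2 = 3.9 to 4.63/0.5 = 9.3 points per SD. These cases are upper bounds. The failure is the same at 25% and 50%.

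**Scope is narrow.** Family functioning is re-measured, and the planned models work for its month-6 or month-12 values. The SAP also calls its models similar to published ones, which leaves some latitude, but the equations it prints are specific.

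**Conclusion.** The concern holds for factors measured only before randomization: cotinine, health literacy, and family functioning if its baseline value is used. For these the planned models credit about 0% of the race difference on average, whether the factor explains none of it or all of it. That direction follows from randomization and the least-squares identity and does not depend on the assumed gaps or shares; the simulated sizes do. The zero expectation applies to all randomized children. Dropout related to arm, race and the factor together could move a3 among completers, but that would be selection and not explanation.

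The harm is limited. The analysis is exploratory, runs only if a race difference is found (stated power 67%), and affects no primary estimate. It should still be corrected, because as written it cannot answer the question the SAP poses for smoke exposure.

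**What to change.** - State at which visit each M is measured.
- For M measured before randomization, replace model (2) with Y = i2 + c1'X + c2'Z + c3'XZ + bM + dXM + e2. Report the drop from c3 to c3' with a bootstrap interval, together with a2 (race-factor association) and d (treatment-by-factor interaction).
- Keep the a3·b path only for M measured after randomization, such as family functioning at month 6 or 12.

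The cost is one model term, a bootstrap interval and a sentence on timing. No new data are needed. Intervals will be wide when the explained share is small, and the report should say so.

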APPENDIX A: PATS VISIT SCHEDULE

	Preliminary Screen		Confirm Final Eligibility	eAT Only	Visits for Both Arms				WWSC Only
Procedures and Assessments	ENT V1	PSG V2	Baseline V3 Randomize V4 ⁷	Surgery V5	Phone ¹²	Interim V6	PSG V7	Endpoint V8	ENT Re-eval
Visit	Screen		Baseline Day 0	eAT Only	Phone	Clinic	PSG	Clinic	WWSC Only
Time	Day -60 to -1		At baseline or within 48 hrs of baseline	M1 W/in 1-4 wk randomiz ed	,M2, M4 ,M8, M10,	M6	M12	M12	1-4 wks after M12
Preliminary eligibility review; informed consent ¹	X	X							
ENT evaluation ²	X								
PSG ³		X					X		
Randomize			X						
Surgery				X					
Re-evaluation for surgery (WWSC only)									WWSC Remind family X If indicated
Urine cotinine ⁴			X						
Resting BP			X			X		X	
Anthropometry			X			X		X	
Physical exam			X						
Behavioral performance testing ⁵				X			X		X
Parent questionnaires ⁶			X			X		X	
Serum IgE ⁴			X						
Healthy sleep education ⁸			X						
Sleep Diary			X			X		X	
Behavioral rating scales: teacher ¹⁰			X			X		X	
Adverse event, medication, and HCU inquiry ¹¹		X	X		X	X		X	

NOTES

1. Preliminary screening/ascertainment of eligibility and the face-to-face consent discussion will occur at slightly different points of participant interaction, depending on the local site's recruitment strategies (sources: ENT, sleep laboratory, other clinics)
2. Existing ENT evaluations (within 90 days prior to randomization) can be utilized to establish primary eligibility for adenotonsillectomy surgical candidacy. WWSC group will be re-evaluated for surgery after month 12 (within 1-4 weeks of the month 12 visits).
3. An overnight PSG must be performed (with 60 days) and approved by the study's reading center prior to randomization. Another PSG is completed at the month 12 endpoint visits for those who are eligible and enrolled in the study.
4. Samples will be processed and stored locally for shipment to the CCC central repository monthly.
5. Child completes 2 behavioral performance tests (coordination, vigilance).
6. Parent completes behavioral rating scales and other questionnaires.
7. Not an actual visit. Listed in the database as Visit 4 for tracking purposes. Randomization is an administrative process that can easily be completed at the end of the baseline visit before the family leave the clinic (ideal).
8. Health sleep habits guidance Actigraph device initialized, verbal and written instructions provided at the baseline, interim, and endpoint visits to be returned in a pre-paid mailer after 1 week of recording at home.
9. Teacher completes 3 behavioral rating scales (BRIEF2/P, Conners, CBCL-TRF) at 3 time points: baseline, month 6 and month 12. Forms are sent (mailed by study staff) immediately after the visit.
10. Adverse event, medication, health care utilization (HCU) inquiries occur at all participant visits (verbally for phone visit; face-to-face for other visit types).
11. Monthly contact by telephone, email and/or text messaging at Months 1,2,3, 4,5,7,8,9, 10,11

